| | | | | Male, Female | | | | | Y/N | |
| | | | | | | | | | | |

¹HOIs for each patient ID listed on separate rows. Patient label is a unique patient identifier for each patient, current ID represents study ID number assigned during current treatment episode in which HOI occurred.

²Treatment Episode may be inclusive of more than 1 vernakalant infusion.

³Based on informed consent dates for each vernakalant treatment episode.

Listing 8 Serious Adverse Events (SAEs) for Patients with Multiple Vernakalant Administrations Enrolled in Registry

| Patient Label ¹ | Current ID Number (Patient ID, Site ID) ¹ | Patient Type | Age (yrs) | Gender | Country | Total Number of Previous Treatment Episode ² | Time (days) between Current and Previous Treatment Episode ³ | MedDRA Term | | | Relatedness | AE outcome |
|----------------------------|--|--------------|-----------|--------------|---------|---|---|-------------|-----|----|-------------|------------|
| | | | | | | | | SOC | HLT | PT | | |
| | | | | Male, Female | | | | | | | | |

| Patient Label ¹ | Current ID Number (Patient ID, Site ID) ¹ | Patient Type | Age (yrs) | Gender | Country | Timing (Min) in relation to start of first infusion | Onset date | Stop date | Contraindication(s) | | SRC HOI Designation | SRC Adjudication Term |
|----------------------------|--|--------------|-----------|--------------|---------|---|------------|-----------|---------------------|--|---------------------|-----------------------|
| | | | | | | | | | Y/N | | | |
| | | | | Male, Female | | | | | | | | |

¹SAEs for each patient ID listed on separate rows. Patient label is a unique patient identifier for each patient, current ID represents study ID number assigned during current vernakalant treatment episode in which SAE occurred.

²Treatment Episode may be inclusive of more than 1 vernakalant infusion.

³Based on informed consent dates for each treatment episode.

Country-Specific Tables

The following tables will be displayed for each country:

- Table 1.2 Use of Pre-Infusion Checklist Prior to Vernakalant IV
- Table 1.3 Receipt of Healthcare Provider (HCP) Educational Card, by Site
- Table 4.1 Patient Demographics
- Table 5 Other Baseline Presenting Conditions and Medical History
- Table 9.1 Vernakalant IV Administration and Dosing (Overall)
- Table 9.2 Vernakalant IV Administration and Dosing (Prospective Patients)
- Table 9.3 Vernakalant IV Administration and Dosing (Retrospective Patients)
- Table 10 Patient Age and Therapeutic Indication for Use in Accordance with the Vernakalant IV Summary of Product Characteristics
- Table 11 Contraindications for Use in Accordance with the Vernakalant IV Summary of Product Characteristics

These country-specific tables will be structured in the same format as the tables for the overall population. The table title will be the original table title plus country name, and the table number for a country-specific table will be like Table x.y, where “Table x” is the number of the original table. For example, if the first country in alphabetical order is Austria, it will be “Table 1.2.1 Use of Pre-Infusion Checklist Prior to Vernakalant IV – Austria”.

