## Vernakalant IV Sterile Concentrate Prospective Safety Registry Study

Sponsor Protocol Identifier: 6621-049-00

3 August 2016

---

also attached to each written answer from the Medical Information Service to healthcare professionals' (HCPs) questions on the use of vernakalant IV.

The risk minimization measure to incorporate a Pre-Infusion Checklist with drug packaging was initiated in 2012. The checklist provides specific instructions on how to determine the eligibility and potential risks of a patient (including contraindications) to be administered vernakalant IV, and for monitoring of the patient for the duration of the infusion and for at least 15 minutes after the completion of the infusion for signs and symptoms of a sudden decrease in blood pressure or heart rate. Within the SmPC, an HCP is reminded to use the Pre-Infusion Checklist before administering vernakalant IV.

The risk minimization plan requires information gathering on whether the risk minimisation tools (Pre-Infusion Checklist and HCP Educational Card) are reaching the target audience and whether they are being used.

The Sponsor, in collaboration with the designated CRO, will conduct a post-authorisation safety study (PASS) of vernakalant IV in order to collect information about normal conditions of use and dosing of vernakalant IV, and to quantify possible medically significant risks of hypotension, ventricular arrhythmia, bradycardia, and atrial flutter in real-world clinical practice. Due to expected limitations of existing registries and electronic healthcare records systems in EU countries (e.g., AFNET, THIN, GPRD, Nordic Country Hospital Registries) for obtaining all data elements necessary to address the study's research objectives, the PASS will employ prospective data collection using a network of clinical sites across multiple countries in the EU.

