### **7.2.1 Required key data elements for retrospective data collection**

The data elements listed in section 7.1.1 will be collected for all patients enrolled retrospectively, with the exception of the following which may not be available retrospectively in the patients' hospital records;

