5.3 Receipt and Use of Risk Minimisation Tools

Data regarding use and receipt of Pre-Infusion Checklist and HCP Educational Card (resulting from Pharmacovigilance Risk Assessment Committee [PRAC] feedback) were collected starting on August 9, 2014. **Table 1.2** includes information on whether the Pre-Infusion Checklist was used prior to vernakalant IV administration, and **Table 1.3** includes information on whether the site investigator and/or co-investigator received and read the HCP Educational Card.

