| Length of stay <24 hours | xx (xx.x%) | xx (xx.x%) | xx (xx.x%) |
| Length of stay >24 hours | xx (xx.x%) | xx (xx.x%) | xx (xx.x%) |
| Missing | xx | xx | xx |
| General medical ward | | | |
| n | XXX | XXX | XXX |
| Mean (SD) | xx.x (xx.x) | xx.x (xx.x) | xx.x (xx.x) |
| Median | XX.X | XX.X | XX.X |
| Q1; Q3 | XX.X, XX.X | XX.X, XX.X | XX.X, XX.X |
| Min, Max | XX.X, XX.X | XX.X, XX.X | XX.X, XX.X |
| Length of stay <24 hours | xx (xx.x%) | xx (xx.x%) | xx (xx.x%) |
| Length of stay >24 hours | xx (xx.x%) | xx (xx.x%) | xx (xx.x%) |
| Missing | xx | xx | xx |
| Other | | | |
| n | XXX | XXX | XXX |
| Mean (SD) | xx.x (xx.x) | xx.x (xx.x) | xx.x (xx.x) |
| Median | XX.X | XX.X | XX.X |
| Q1; Q3 | XX.X, XX.X | XX.X, XX.X | XX.X, XX.X |
| Min, Max | XX.X, XX.X | XX.X, XX.X | XX.X, XX.X |
| Length of stay <24 hours | xx (xx.x%) | xx (xx.x%) | xx (xx.x%) |
| Length of stay >24 hours | xx (xx.x%) | xx (xx.x%) | xx (xx.x%) |
| Missing | xx | xx | xx |

Note: Total n for each variable includes non-missing observations. Percentages, where applicable, are calculated with non-missing observations in denominator unless otherwise noted.

¹ Hospital size based on number of beds. Large hospitals defined as 300 or more beds; small hospitals defined as fewer than 300 beds.

Table 1.2 Use of Pre-Infusion Checklist Prior to Vernakalant IV Administration

| Characteristic | Analysis Set (N = xxx)¹ | Prospective Patients (N = xxx)¹ | Retrospective Patients (N = xxx)¹ |
|-----------------------|---|---|---|
| n | xxx | xxx | xxx |
| Yes | xx (xx.x%) | xx (xx.x%) | xx (xx.x%) |
| No | xx (xx.x%) | xx (xx.x%) | xx (xx.x%) |
| Don't know | xx (xx.x%) | xx (xx.x%) | xx (xx.x%) |

Note: Total n for each variable includes non-missing observations. Percentages, where applicable, are calculated with non-missing observations in denominator unless otherwise noted.

¹ Patients with available data on usage of Pre-infusion Checklist. For prospective patients data collection regarding the Pre-infusion Checklist was initiated on August 9, 2014.

Table 1.3 Receipt of Healthcare Provider (HCP) Educational Card, by Site

| Characteristic | Number of Unique Sites in Analysis Set (N=xx) ¹ |
|--|--|
| Investigator and/or co-investigator received the HCP Educational Card² | |
| n | xxx |
| Yes | xx (xx.x%) |
| No | xx (xx.x%) |
| Don't know | xx (xx.x%) |
| Missing | xx |
| Investigator and/or co-investigator read the HCP Educational Card² | |
| n | xxx |
| Yes | xx (xx.x%) |

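### Table 1.2 reports Pre-Infusion Checklist use only among patients with an answer and shows no missing count, so possible bias in the figure cannot be assessed

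*SAP*

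**What the plan says.** Protocol section 3 says the risk minimisation plan requires information on whether the tools "are reaching the target audience and whether they are being used". SAP 5.3 assigns the checklist part to Table 1.2, which is to show "whether the Pre-Infusion Checklist was used prior to vernakalant IV administration". SAP 4.3 has the table repeated for each country.

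The shell in SAP Appendix 1 has columns for the analysis set, prospective patients and retrospective patients. Its rows are n, Yes, No and Don't know. Footnote 1 is attached to N in all three columns and defines it as "Patients with available data on usage of Pre-infusion Checklist". The same footnote adds: "For prospective patients data collection regarding the Pre-infusion Checklist was initiated on August 9, 2014". The general note under the table states the percentage rule: "Percentages, where applicable, are calculated with non-missing observations in denominator unless otherwise noted".

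SAP 4.4 allows no imputation. Table 18, which counts missing values for selected critical fields, has no row for checklist use.

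For retrospective patients, Protocol 7.2.1 states: "The data elements listed in section 7.1.1 will be collected for all patients enrolled retrospectively, with the exception of the following". Checklist use is among the elements in 7.1.1 and is not among the listed exceptions.

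**The concern.** A percentage of use is informative only if the reader can see whom it describes. Here the base is fixed by whether an answer exists, so blank forms leave both numerator and denominator, and the table does not say how many there are. The question put to this registry is whether the tool is being used in practice, and Table 1.2 is the only place that answers it for the checklist. A regulator would see a percentage of those who answered, without the number of patients for whom an answer was due.

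**Working it through.** No checklist-use figure, missing rate or target is stated in the documents, so there is nothing to reproduce. The check has three parts.

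**1. The shell against its neighbours.** Because N is already limited to patients with data, N and n are equal by construction, and a Missing row added to the shell as it stands would be empty. Table 1.1 has Missing rows. Table 1.3 (educational card, by site) has them too, although its N is also limited to sites with available data. Table 11, another patient-level table serving Primary Objective 3, prints Missing/Unknown with a percentage. The rows of Table 18 are height, NYHA class, smoking, infusion stop time, time to cardioversion, and blood pressure and rhythm monitoring.

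**2. What can be recovered by subtraction.** Tables 2 and 3 give analysis-set counts by method of enrolment.

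- *Retrospective column.* Protocol 7.2 admits only patients treated since April 2013. Protocol section 3 says: "The risk minimization measure to incorporate a Pre-Infusion Checklist with drug packaging was initiated in 2012". Every retrospective episode is therefore eligible for the question, and footnote 1 gives no collection start date for this group. Analysis-set N minus Table 1.2 N is the number without an answer.
- *Prospective column.* The same subtraction gives E + B, where E is the number treated before 9 August 2014 (never asked) and B is the number treated on or after that date and left blank. No shell splits prospective patients at that date. The title of Table 3 mentions enrolment period, but its columns show only enrolment method. B cannot be separated from E.

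**3. What an unknown missing share does to the estimate.** Let a be the share of eligible episodes with an answer, p the Yes share among them, and q the use among those without an answer. None of the three is in the documents, so the values below are assumptions.

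- Reported use = p
- Use among all eligible = a·p + (1 − a)·q
- Overstatement = p − [a·p + (1 − a)·q] = (1 − a)(p − q)

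The overstatement is positive if q < p, zero if q = p and negative if q > p. With p = 60%:

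| a | Use if q = 0 (a·p) | Use if q = 1 (a·p + 1 − a) | Overstatement if q = p/2 |
|---|---|---|---|
| 0.95 | 57% | 62% | 1.5 points |
| 0.90 | 54% | 64% | 3 points |
| 0.70 | 42% | 72% | 9 points |
| 0.50 | 30% | 80% | 15 points |

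The width of each range is 1 − a, which is the quantity Table 1.2 leaves out. At a = 0.70 the reported 60% could be 18 points too high (60 − 42) or 12 points too low (72 − 60).

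The bounds count Don't know as not Yes, as the shell does, because Don't know carries a percentage and stays in the denominator. With assumed counts of 60 Yes, 30 No and 10 Don't know, Yes is 60/100 = 60.0%. Dropping Don't know would give 60/90 = 66.7%.

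**The case against.** The strongest defence is that the restriction has a stated and sensible reason. Prospective patients treated before 9 August 2014 were not asked, whatever they did. Counting them as non-users would bias use downward, and anyone treated before the checklist existed could not have used it. Don't know is kept in the denominator and is a natural entry for a silent chart, which works against inflation. N and n are printed, and the retrospective gap follows by subtraction. The rows of Table 18 match the elements that Protocol 7.2.1 says may be unavailable retrospectively, so leaving out the checklist looks deliberate. Protocol 11.5 plans eCRF edits that flag missing data. Checklist use is also one descriptive item among several under Primary Objective 3, with no target or test.

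Most of this stands, and it rules out a stronger reading. A reader might infer that reported use is likely to be overstated, on the view that an undocumented checklist was probably an unused one. The documents do not say that. Overstatement needs lower use among patients without an answer. That is plausible, mainly for retrospective charts if use was written down more often than non-use, but it is an assumption.

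The defence does not cover prospective item non-response. The date restriction justifies leaving out E; it does not justify hiding B. Don't know covers recorded answers, not blank fields. The absence of an exemption in Protocol 7.2.1 also means that a blank is a gap to be reported. The protocol itself accepts in 7.2 that retrospective inclusion could increase missing data, and Appendix I plans 435 of the remaining 810 enrolments (435/810 = 54%) as retrospective.

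**Conclusion.** The point holds as a reporting weakness of moderate to minor weight. Table 1.2 hides the extent of missing checklist data. In the prospective column, and so in the overall column, non-response cannot be separated from data never collected. Any bias in reported use therefore cannot be assessed.

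Neither the direction nor the size of a bias is established. The ranges above rest on assumed values of a, p and q. They show only that the uncertainty in percentage points equals the undisclosed missing share. If that share is about 5%, little is at stake. If it is 30% or more, the printed percentage says little about use in all eligible patients. The matter bears on Primary Objective 3 only. HOI incidence is unaffected.

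**What to change.** - **Table 1.2, and its country versions.** Set the base to eligible episodes: prospective episodes treated on or after 9 August 2014, and all retrospective episodes. State separately the number of prospective episodes not collected by design. Add a Missing row.
- **Percentages.** Give Yes as a percentage of all eligible episodes, labelled as a lower bound on use, next to Yes as a percentage of those with an answer.
- **Table 18.** Add a row for checklist use, on the same eligible base.
- **Table 1.3.** The Missing rows are already there. Change only N, to all sites in the analysis set, and mark those not asked by design.

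This needs no new data and changes no other analysis. The cost is a shell and programming edit, and possibly a less favourable printed percentage.

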4.2 Analysis Populations

All screened patients will be included in summary of patient disposition with additional summary of their demographic characteristics. All enrolled patients who meet the eligibility criteria, sign the informed consent form, and are administered vernakalant IV will be included in the analysis population set, regardless of their disposition status. If a patient's consent is withdrawn prior to completing follow-up period, all data already collected as part of the study will be retained for analysis unless country-specific ethics committee (EC) requirements prohibit this or the patient requests otherwise. In addition, patients who discontinue from the study prior to receiving vernakalant administration will not be included in the overall analysis population. All the summaries will be presented on the overall analysis population set unless otherwise stated.

Patients may be enrolled in the study more than once in association with multiple administrations of vernakalant IV. Patients with multiple enrolments are included in the analysis population, and the number of previous study enrolments is provided in the study analysis. All study analyses presented in the study tables, listings, and figures of this report treat each patient's subsequent administrations of vernakalant IV as occurring independently.

Effectiveness analysis population is defined as all patients from overall analysis population defined above EXCEPT those who receive ECV or IV Class I/III AA for cardioversion within 90 minutes of start of the first vernakalant IV administration. But for analysis of the effectiveness of

vernkalant IV, e.g., rate of conversion, both analysis population and effectiveness population may be used.

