Note: Total n for each variable includes non-missing observations. Percentages, where applicable, are calculated with non-missing observations in denominator unless otherwise noted.

¹Analysis population set is defined as all treatment episodes among enrolled patients who meet the eligibility criteria and sign the informed consent form and are administered vernakalant IV.

²Number of patients with multiple enrolments in SPECTRUM.

³Effectiveness analysis population set is defined as all treatment episodes among patients from the analysis population set except for those treatment episodes in which patients receive another therapy for cardioversion within 90 minutes of start of the first vernakalant IV administration (i.e. electrical or pharmacologic cardioversion).

⁴Includes patients with single or multiple enrolments.

⁵Patients who discontinued the study for any reason or who did not have a complete end of study form as of the time of data extraction for interim reports.

Table 3 Overview of Enrolled Patients in the Analysis Set by Enrolment Period and Country

| Country | Analysis Set (N = xxx) | Prospective Patients (N = xxx) | Retrospective Patients (N = xxx) |
|-----------|---------------------------|-----------------------------------|-------------------------------------|
| Country 1 | xx (xx.x%) | xx (xx.x%) | xx (xx.x%) |
| | | | |
| Country 2 | xx (xx.x%) | xx (xx.x%) | xx (xx.x%) |
| | | | |
| Country 3 | xx (xx.x%) | xx (xx.x%) | xx (xx.x%) |
| | | | |
| Etc. | | | |

Note: Total n for each variable includes non-missing observations. Percentages, where applicable, are calculated with non-missing observations in denominator unless otherwise noted.

Table 4.1 Patient Demographics, All Enrolled Patients

| Characteristic | Analysis Set (N = xxx) | Prospective Patients (N = xxx) | Retrospective Patients (N = xxx) |
|---|---------------------------|-----------------------------------|-------------------------------------|
| Age (years) | | | |
| n | XXX | XXX | XXX |
| Mean (SD) | xx.x (xx.xx) | xx.x (xx.xx) | xx.x (xx.xx) |
| Median | xx.x | xx.x | xx.x |
| Q1, Q3 | xx.x, xx.x | xx.x, xx.x | xx.x, xx.x |
| Min, Max | xx.x, xx.x | xx.x, xx.x | xx.x, xx.x |
| Missing | xx | xx | xx |
| Gender | | | |
| n | XXX | XXX | XXX |
| Male | xx (xx.x%) | xx (xx.x%) | xx (xx.x%) |
| Female | xx (xx.x%) | xx (xx.x%) | xx (xx.x%) |
| Missing | xx | xx | xx |
| Race¹ | | | |
| n | XXX | XXX | XXX |
| White | xx (xx.x%) | xx (xx.x%) | xx (xx.x%) |

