| Time to conversion (minutes) from start of first infusion (among patients with conversion to sinus rhythm for at least 1 minute within 90 minutes from start of first infusion within the effectiveness analysis population) | All responders | Responde rs (receiving 1 infusion) | Responde rs (receiving 2 infusions ¹) | All responder s | Responde rs (receiving 1 infusion) | Responde rs (receiving 2 infusions ¹) | All responders | Responde rs (receiving 1 infusion) | Responde rs (receiving 2 infusions ¹) |
| n | xx | xx | xx | xx | xx | xx | xx | xx | xx |
| Mean (SD) | xx.x (xx.xx) | xx.x (xx.xx) | xx.x (xx.xx) | xx.x (xx.xx) | xx.x (xx.xx) | xx.x (xx.xx) | xx.x (xx.xx) | xx.x (xx.xx) | xx.x (xx.xx) |
| Median | xx.x | xx.x | xx.x | xx.x | xx.x | xx.x | xx.x | xx.x | xx.x |

| | | | | | | | | | |
|---|------------------------|--|---|------------------------|--|---|------------------------|--|---|
| Q1, Q3 | xx.x, xx.x | xx.x, xx.x | xx.x, xx.x | xx.x, xx.x | xx.x, xx.x | xx.x, xx.x | xx.x, xx.x | xx.x, xx.x | xx.x, xx.x |
| Min, Max | xx, xx | xx, xx | xx, xx | xx, xx | xx, xx | xx, xx | xx, xx | xx, xx | xx, xx |
| Missing | xx | xx | xx | xx | xx | xx | xx | xx | xx |
| Conversion to sinus rhythm for at least 1 minute within 90 minutes from start of first infusion among all patients receiving vernakalant excluding those who received ECV or IV Class I/III AA within 90 minutes of vernakalant administration³ | | | | | | | | | |
| n | xx | | | xx | | | xx | | |
| Yes, n (%) [95% CI]) ³ | xx (xx.x [xx.x, xx.x]) | | | xx (xx.x [xx.x, xx.x]) | | | xx (xx.x [xx.x, xx.x]) | | |
| Time to conversion (minutes) from start of first infusion (among patients with conversion to sinus rhythm for at least 1 minute within 90 minutes from start of first infusion among all patients receiving vernakalant | All responders | Responders (receiving 1 infusion) | Responders (receiving 2 infusions) | All responder s | Responders (receiving 1 infusion) | Responders (receiving 2 infusions) | All responders | Responders (receiving 1 infusion) | Responders (receiving 2 infusions) |

| | | | | | | | | | |
|--|------------------------------|-----------------|-----------------|------------------------------|-----------------|-----------------|---------------------------|-----------------|-----------------|
| excluding those who received ECV or IV Class I/III AA within 90 minutes of vernakalant administration) | | | | | | | | | |
| n | xx | xx | xx | xx | xx | xx | xx | xx | xx |

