| Mean (SD) | xx.x (xx.xx) | xx.x (xx.xx) | xx.x (xx.xx) | xx.x (xx.xx) | xx.x (xx.xx) | xx.x (xx.xx) | xx.x (xx.xx) | xx.x (xx.xx) | xx.x (xx.xx) |
| Median | xx.x | xx.x | xx.x | xx.x | xx.x | xx.x | xx.x | xx.x | xx.x |
| Q1, Q3 | xx.x, xx.x | xx.x, xx.x | xx.x, xx.x | xx.x, xx.x | xx.x, xx.x | xx.x, xx.x | xx.x, xx.x | xx.x, xx.x | xx.x, xx.x |
| Min, Max | xx, xx | xx, xx | xx, xx | xx, xx | xx, xx | xx, xx | xx, xx | xx, xx | xx, xx |
| Missing | xx | xx | xx | xx | xx | xx | xx | xx | xx |
| Conversion to sinus rhythm for at least 1 minute within 90 minutes from start of first infusion among all patients receiving vernakalant excluding those who received ECV or oral propafenone/flecainide or IV Class I/III AA within 90 minutes of vernakalant administration⁴ | | | | | | | | | |
| n | xx | | | xx | | | xx | | |
| Yes, n (%) [95% CI] ⁴ | xx (xx.x [xx.x, xx.x]) | | | xx (xx.x [xx.x, xx.x]) | | | xx (xx.x [xx.x, xx.x]) | | |

| Time to conversion (minutes) from start of first infusion (among patients with conversion to sinus rhythm for at least 1 minute within 90 minutes from start of first infusion among all patients receiving vernakalant excluding those who received ECV or oral propafenone/flecainide or IV Class I/III AA within 90 minutes of vernakalant administration) | All responders | Responders (receiving 1 infusion) ¹ | Responders (receiving 2 infusions) ¹ | All responders | Responders (receiving 1 infusion) | Responders (receiving 2 infusions) ¹ | All responders | Responders (receiving 1 infusion) | Responders (receiving 2 infusions) ¹ |
|---|----------------|--|---|----------------|-----------------------------------|---|----------------|-----------------------------------|---|
| n | XX | XX | XX | XX | XX | XX | XX | XX | XX |
| Mean (SD) | XX.X (xx.xx) | XX.X (xx.xx) | XX.X (xx.xx) | XX.X (xx.xx) | XX.X (xx.xx) | XX.X (xx.xx) | XX.X (xx.xx) | XX.X (xx.xx) | XX.X (xx.xx) |
| Median | XX.X | XX.X | XX.X | XX.X | XX.X | XX.X | XX.X | XX.X | XX.X |
| Q1, Q3 | XX.X, XX.X | XX.X, XX.X | XX.X, XX.X | XX.X, XX.X | XX.X, XX.X | XX.X, XX.X | XX.X, XX.X | XX.X, XX.X | XX.X, XX.X |
| Min, Max | XX, XX | XX, XX | XX, XX | XX, XX | XX, XX | XX, XX | XX, XX | XX, XX | XX, XX |
| Missing | XX | XX | XX | XX | XX | XX | XX | XX | XX |

Note: Total n for each variable includes non-missing observations. Percentages, where applicable, are calculated with non-missing observations in denominator unless otherwise noted.

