¹ Includes patients who receive more than 1 infusion within a single treatment episode.

² Rate of conversion (%) is calculated as: (number of patients who have conversion to sinus rhythm for at least one minute with 90 minutes after first vernakalant infusion within effectiveness analysis population) / (total number of patients within effectiveness analysis population) x 100.

³ Rate of conversion (%) is calculated as: (number of patients who, within 90 minutes after first vernakalant infusion, have conversion to sinus rhythm for at least one minute but have no ECV or IV Class I/III AA within overall analysis population) / (total number of patients within overall analysis population).

⁴ Rate of conversion (%) is calculated as: (number of patients who, within 90 minutes after first vernakalant infusion, have conversion to sinus rhythm for at least one minute but have no ECV, oral propafenone/flecainide or IV Class I/III AA within overall analysis population) / (total number of patients within overall analysis population).

Template of Table 15a will be applied to the following three tables.

Table 15b Proportion of Patients Converted to Sinus Rhythm and Time to Conversion Following Vernakalant Infusion (SmPC Subgroup Analysis)

Table 15c Proportion of Patients Converted to Sinus Rhythm and Time to Conversion Following Vernakalant Infusion (Non-Surgery Patients)

Table 15d Proportion of Patients Converted to Sinus Rhythm and Time to Conversion Following Vernakalant Infusion (Post-Cardiac Surgery Patients)

Table 16.1a.1 Serious Adverse Events (System Organ Class and Preferred Term) by Outcome (Analysis Set) – Investigator Assessment

| | Analysis Set (N=xxx) Outcome | | | | | | | |
|---|---|----------|---|----------|---|----------|---|----------|
| | Recovered | | Recovered with Sequelae | | Not Recovered | | Overall | |
| System Organ Class/ High Level Term/ Preferred Term | Patients n (Cumulative Incidence ¹) | Events n | Patients n (Cumulative Incidence ¹) | Events n | Patients n (Cumulative Incidence ¹) | Events n | Patients n (Cumulative Incidence ¹) | Events n |
| Any SAE | xx (x.x%) | xx |
| SOC 1 | xx (x.x%) | xx |
| HLT 1 | xx (x.x%) | xx |
| PT 1 | xx (x.x%) | xx |
| PT 2 | xx (x.x%) | xx |
| SOC 2 | xx (x.x%) | xx |
| HLT 2 | xx (x.x%) | xx |
| PT 1 | xx (x.x%) | xx |
| PT 2 | xx (x.x%) | xx |

Note: SAE events include reported HOIs that are mapped to specific MedDRA terms.

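### SAP Table 15a: the labels of blocks 2 and 3 remove rescued patients, footnotes 3 and 4 keep them in the denominator, and two promised conversion rates have no row

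*SAP*

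**What the plan says.** Protocol 9.1 defines effectiveness as the proportion of patients in sinus rhythm for at least one minute within 90 minutes of the start of the first administration. Protocol 10.1 analyses all enrolled patients documented as treated. SAP 3.4 gives the matching formula: relevant patients converted, over relevant patients given vernakalant. Neither puts a condition on other cardioversion treatment.

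SAP 4.2 adds an effectiveness population, which is the analysis population "EXCEPT those who receive ECV or IV Class I/III AA for cardioversion within 90 minutes of start of the first vernakalant IV administration". Table 2, footnote 3, defines the same population as all treatment episodes "except for those treatment episodes in which patients receive another therapy for cardioversion within 90 minutes of start of the first vernakalant IV administration", glossed as "i.e. electrical or pharmacologic cardioversion".

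SAP 5.10 commits to the 90-minute rate in both populations, citing Table 15a, and to a rate without time restriction. SAP 3.3 makes the second promise too.

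Table 15a has three rate blocks:

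- Block 1 is the effectiveness population (footnote 2).
- Block 2 is labelled as conversion "among all patients receiving vernakalant excluding those who received ECV or IV Class I/III AA within 90 minutes of vernakalant administration". Footnote 3 gives its rate as patients who convert "but have no ECV or IV Class I/III AA within overall analysis population) / (total number of patients within overall analysis population".
- Block 3 is labelled as "excluding those who received ECV or oral propafenone/flecainide or IV Class I/III AA within 90 minutes of vernakalant administration". The footnote 4 numerator is patients who convert "but have no ECV, oral propafenone/flecainide or IV Class I/III AA within overall analysis population", again over the total analysis population.

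For Tables 15b-15d the instruction is "Template of Table 15a will be applied to the following three tables".

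**The concern.** Below, rescued means given one of the listed treatments within 90 minutes. Under the label, a rescued patient is outside the table block. Under the footnote, the same patient is in the denominator as a non-converter. One result line therefore has two definitions, and its percentage and confidence interval depend on which one the programmer follows. The SAP clearly expects some rescue: it builds a population around it, and Tables 12a and 13a have 90-minute columns for other IV anti-arrhythmics and for ECV.

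The rate that the protocol defines, and that 5.10 promises for the analysis population, also appears to have no line of its own. A reader could take a block that removes rescued patients, or counts them as failures, for the protocol endpoint.

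**Working it through.** The documents state no conversion rate, rescue share or precision target for this endpoint in the registry, so there is no plan figure to reproduce. The check compares definitions and then applies simple algebra.

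**1. Denominators and numerators**

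| Row | Denominator | Rescued patients in numerator? |
|---|---|---|
| Block 1 (footnote 2) | effectiveness population | no, not in the population |
| Block 2 by label | all treated minus rescued | no, not in the population |
| Block 2 by footnote 3 | all treated | no, but still in the denominator |
| Block 3 by label | all treated minus rescued (oral drugs included) | no, not in the population |
| Block 3 by footnote 4 | all treated | no, but still in the denominator |
| Protocol 9.1 / SAP 3.4 | all treated | yes, if converted within 90 minutes |

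Read by its label, block 2 is almost block 1 again. What separates them is the for-cardioversion qualifier, present in SAP 4.2 and absent from the labels and footnotes 3 and 4, and the time origin. SAP 4.2 counts from the start of the first administration, the labels count from administration, and the footnotes count from the first infusion.

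**2. Label against footnote.** Let N be the patients treated, r the share rescued and x the unrescued converters.

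- Label rate = x / [N(1 − r)]
- Footnote rate = x / N
- Label rate = footnote rate / (1 − r)

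This ratio needs no assumption about which patients are rescued. Take N = 2,000 (the target) and x = 1,000, a footnote rate of 50%, with r assumed:

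| r (assumed) | Label rate |
|---|---|
| 2% | 1,000/1,960 = 51.0% |
| 5% | 1,000/1,900 = 52.6% |
| 10% | 1,000/1,800 = 55.6% |
| 20% | 1,000/1,600 = 62.5% |

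**3. Footnote 3 against Protocol 9.1.** Take N = 2,000 and r = 10% (200 rescued, 1,800 not). Assume 51.1% conversion among the unrescued, borrowing the phase III figure in Protocol section 3, so x = 920.

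- Block 2 by label: 920/1,800 = 51.1% (Clopper-Pearson 95% CI 48.8 to 53.4)
- Block 2 by footnote 3: 920/2,000 = 46.0% (43.8 to 48.2)
- Protocol 9.1, if 0%, 50% or 90% of the 200 rescued were in sinus rhythm for a minute within the window: 920/2,000 = 46.0%, 1,020/2,000 = 51.0% or 1,100/2,000 = 55.0%

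Footnote 3 equals the protocol rate only when no rescued patient converted in the window. Otherwise it is lower.

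**4. Rows present.** Rate footnotes 2, 3 and 4 map one-to-one to the three blocks, so the shell looks complete as extracted. All three blocks are limited to 90 minutes and all three act on rescue. Neither the unconditioned analysis-population rate nor the any-time rate has a row.

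**5. Effectiveness population.** SAP 4.2 removes patients given ECV or IV class I/III drugs for cardioversion. Table 2, footnote 3, removes any electrical or pharmacologic cardioversion, which would also take in oral drugs and other classes. The Table 2 count and the block 1 denominator can therefore differ.

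**6. Tables 15b-15d.** Footnotes 3 and 4 confine both numerator and denominator to the overall analysis population. Carried over unchanged, they would repeat the Table 15a rate under a subgroup title.

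**The case against.** The strongest reply is that this is a label clean-up. The footnote markers sit on the result rows and give explicit formulas, and the footnote reading is the only one that gives block 2 a purpose. That is a good guide to intent, and the fix follows it. It does not remove the conflict, because the labels describe another population.

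A second reply is that footnote 3 already supplies the analysis-population rate, with rescue counted as non-conversion. That is a defensible rate, but it is not the one in Protocol 9.1 and SAP 3.4.

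A third reply is that much is visible elsewhere. This stands. Table 2 gives the size of the effectiveness population by enrolment method, Tables 12a and 13a show 90-minute rescue, and Table 18 counts missing conversion times by enrolment method.

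Some stronger readings are not supported:

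- A reader might infer that Table 15d would divide post-surgery converters by all patients and print an absurdly low rate. Footnote 3 pairs no subgroup numerator with an overall denominator, and SAP 3.4 points to the relevant patients as the denominator.
- A reader might infer from the shell's general note that non-missing denominators apply. That note gives way where another rule is stated, and SAP 3.4 and footnotes 2-4 state total patients. What stays open is how a patient without usable times is classified.
- A reader might infer that block 1 must read high. That depends on whether converters are rescued less often than non-converters, and the documents give neither share.

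**Conclusion.** Table 15a is inconsistent as written. Blocks 2 and 3 each carry two definitions whose results differ by the factor 1/(1 − r). Two promised rates have no row, the effectiveness population has two definitions, and the footnotes were not adapted for Tables 15b-15d. The factor is exact; its size is unknown because r is not given. Every percentage above rests on assumed values of r and of conversion, and the Protocol 9.1 range also on an assumed share of rescued patients who convert.

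Severity is minor. The endpoint is secondary and descriptive, and the HOI analyses do not use these rows. The text does not require any one of these rates to be named the main estimate. Nor does it require a row crediting conversion before rescue, or an SmPC subgroup restricted to pre-dose criteria. Those would be optional additions, since SAP 4.3 prespecifies the subgroup with its four-hour clause.

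**What to change.** Change the shells and SAP wording only:

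- **Blocks 2 and 3.** Relabel to match footnotes 3 and 4: all treated, with rescued patients counted as non-converted. Use one for-cardioversion qualifier and one time origin throughout.
- **Protocol rate.** Add a row for the Protocol 9.1 all-treated rate beside the footnote 3 rate, noting that it may include conversions produced by rescue.
- **Any-time rate.** Add the row, or delete the promise from both SAP 3.3 and 5.10.
- **Effectiveness population.** Use a single definition in SAP 4.2 and Table 2, footnote 3.
- **Tables 15b-15d.** Replace the overall analysis population in the footnotes with the table's own subgroup, as SAP 3.4 implies.
- **Missing times.** Keep the total-patient denominator of SAP 3.4 and footnotes 2-4. State how patients without usable times are classified, and refer to Table 18 for their number. Protocol 7.2.1 warns that time to conversion may be unavailable for retrospective patients.

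No new data, imputation or change in conduct is needed. The cost is a few more table rows, and some printed rates slightly lower than the label reading would give.
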